#### 9. STATISTICAL METHODOLOGY

#### 9.1 General

Data listings will be provided for all data that are databased. Summary statistics and statistical analysis will only be presented for data where detailed in this SAP. For continuous data, summary statistics will include the arithmetic mean, arithmetic SD, median, min, max and N. For categorical data, frequency count and percentages will be presented. Data listings will be provided for all subjects up to the point of withdrawal, with any subjects excluded from the relevant population highlighted. Summary statistics and statistical analyses will generally only be performed for subjects included in the relevant analysis population. For the calculation of summary statistics and statistical analysis, unrounded data will be used.

Final, 8 January 2019 Page 6 of 10

Mean change from baseline is the mean of all individual subjects' change from baseline values. Each individual change from baseline will be calculated by subtracting the individual subject's baseline value from the value at the timepoint. The individual subject's change from baseline values will be used to calculate the mean change from baseline using a SAS procedure such as Proc Univariate.

Data analysis will be performed using SAS® Version 9.4 or greater.

## 9.2 Demographics and Subject Disposition

Subject disposition will be listed. The demographic variables age, sex, race, ethnicity, country of enrolment, site ID, body weight, height and body mass index will be summarized and listed.

## 9.3 Safety and Tolerability Assessments

#### 9.3.1 Adverse events

Where changes in severity are recorded in the Case Report Form (CRF), each separate severity of the adverse event (AE) will be reported in the listings, only the most severe will be used in the summary tables. A pre-existing condition is defined as an AE that starts before the subject has provided written informed consent and is ongoing at consent. A non-treatment emergent AE is defined as an AE which starts after informed consent but prior to the first dose. A treatment-emergent AE is defined as an AE which occurs postdose or which is present prior to dosing and becomes more severe postdose.

All AEs will be listed. Treatment-emergent AEs will be summarized by formulation and severity. The frequency (the number of AEs, the number of subjects experiencing an AE and the percentage of subjects experiencing an AE) of treatment-emergent AEs will be summarized by formulation, Medical Dictionary for Regulatory Activities (MedDRA) version 21.0 system organ class and preferred term. The summary and frequency AE tables will be presented for all causalities. Any serious AEs will be listed.

#### 9.3.2 Concomitant medication

Concomitant medication will be coded using the WHO drug dictionary (Version March 2018). Concomitant medication will be listed.

#### 9.3.3 Clinical laboratory parameters

Additionally clinical chemistry, hematology and urinalysis data outside the reference ranges will be listed.

#### 9.3.4 Vital signs

Vital signs data will be summarized by treatment.

Vital signs data will be listed for individual subjects.

Final, 8 January 2019 Page 7 of 10

# 9.3.5 Electrocardiogram (ECG)

ECGs will be performed for safety monitoring purposes only and will not be presented. Any clinically significant findings from ECGs will be reported as an AE.

# 9.3.6 Hepatic Monitoring

If a subject experiences elevated alanine aminotransferase (ALT)  $\ge 3 \times$  upper limit of normal (ULN), alkaline phosphatase (ALP)  $\ge 2 \times$  ULN, or elevated total bilirubin (TBL)  $\ge 2 \times$  ULN, liver tests will be performed to confirm the abnormality. Additional safety data may be collected if required, as defined in the protocol. Where applicable, the following will be presented.

The subjects' liver disease history and associated person liver disease history data will be listed. Any concomitant medication of acetaminophen/paracetamol will be listed. Results from any hepatic monitoring procedures, such as a magnetic resonance elastography (MRE) scan, and a biopsy assessment will be listed, if performed.

Hepatic risk factor assessment data will be listed. Liver related signs and symptoms data will be summarized by formulation and listed. Alcohol and recreational drug use data will also be listed.

All hepatic chemistry, hematology, coagulation, and serology data will be listed. Values outside the reference ranges will be flagged on the individual subject data listings.

## 9.3.7 Columbia Suicide Severity Rating Scale (C-SSRS)/ Self-Harm Supplement

Given that few or no suicidal ideation or behaviours are anticipated, a listing of C-SSRS data will be produced by subject and visit. Only subjects that show suicidal ideation/behavior or self-injurious behavior without suicidal intent will be reviewed (i.e., if a subject's answers are all 'no' for the C-SSRS, then that subject will not be displayed). However, if a subject reported any suicidal ideation/ behavior or self-injurious behavior without suicidal intent at any time point then all their ideation and behavior will be reviewed, even if not positive.

#### 9.3.8 Hospital Anxiety Depression Scale (HADS)

Data from the HADS assessment will be listed for individual subjects with HADS depression sub-scale  $\geq$ 11 at any time.

#### 9.3.9 Injection Site Assessments

Injection sites will be assessed for induration, swelling, pruritus, and erythema/redness. Data will be summarized in a frequency table by formulation, and listed for individual subjects.

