Injection-Site Bleeding/Bruising Assessment (Minutes)			0, 10, 20, 30, 60, 120, 240		0, 10, 20, 30, 60, 120, 240		0, 10, 20, 30, 60, 120, 240	X		X				Observational assessment of injection-site bleeding and bruising. 0-minute time point should be done within 1 minute following injection; within ± 2 minutes of the 10, 20, and 30-minute time points; within ± 5 minutes of the 60, 120, and 240-minute time points.
Pharmacokinetic Sample								X					X	Samples to be stored only.
Immunogenicity Sample		X						X					X	Samples to be stored only.
Vital Signs (Sitting)	X	X	P, 2-4	Х	P, 2-4	Х	P, 2-4	X		X			Х	Day 1, 8, and 15: 2-4 hour assessment to be conducted at least 2 hours postdose and prior to discharge at approximately 4 hours postdose. Sitting blood pressure and pulse rate may be measured as clinically indicated. Timepoints may be added if warranted.

	Screening				Study Day								FU/ ED ^a	Comments
Procedure	-28 to -2 days prior to Day 1	Day -1	Day 1	Day 7	Day 8	Day 14	Day 15	Day 21 (± 1 day)	Days 28 & 35 (± 3 days)	Day 43 (± 3 days)	Days 50, 57, & 64 (± 3 days)	Day 71 (± 3 days)		
Pharmacogenetic Sample		X												
Adverse Events and Concomitant Medication	X	X	X	X	X	X	X	X	X	X	X	X	X	

Abbreviations: CRU = clinical research unit; C-SSRS = Columbia Suicide Severity Rating Scale; ECG = electrocardiogram; ED = early discontinuation; FSH = follicle-stimulating hormone; FU = follow-up; HADS = Hospital Anxiety and Depression Scale; P = predose; TB = tuberculosis; TST = tuberculin skin test; VAS = visual analog scale.

Note: if multiple procedures take place at the same time point, the following order should be used: ECG, vital signs, and venipuncture.

^a Follow-up / Early Discontinuation should be \sim 12 weeks post last injection (\pm 1 week).

3. Introduction

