9.4.5. Other Tests

9.4.5.1. Injection-Site Assessments

Injection-site assessments will be performed at the times indicated in the Schedule of Activities (Section 2).

If the investigator determines that any ISR is clinically significant or if a subject indicates symptoms are indicative of an ISR (unsolicited event; volunteered by subject), the event will be captured as an AE.

Induration, swelling, pruritus, and erythema/redness associated with study injection sites will be evaluated by the blinded assessor.

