9.4.5.2. Bleeding/Bruising Assessment

All injection sites will be observed at the times indicated in the Schedule of Activities (Section 2) by the blinded assessor, and the presence of visible bleeding/bruising will be recorded on the eCRF. A bandage may be placed on the injection site after assessment.

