10.3.1.2.2. Statistical Evaluation of Other Safety Parameters

Abnormal lab values will be listed. Other safety parameters that will be assessed include injection-site assessments, including pain, induration, swelling, pruritus, bleeding/bruising, and erythema/redness. The parameters will be listed and summarized using standard descriptive statistics. Suicidal ideation and/or behavior and self-injurious behavior with no suicidal intent, based on the C-SSRS, will be listed by subject. Only subjects that show suicidal ideation/behavior or self-injurious behavior without suicidal intent will be included in the listing (ie, if a subject answers are all 'no' for the C-SSRS, then that subject will not be displayed). HADS item scores will be listed for subjects with HADS depression sub-scale ≥11 at any time. Additional analyses may be performed if warranted upon review of the data.

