#### 3. INTRODUCTION

This SAP has been developed after review of the Clinical Study Protocol (final version dated 29 October 2018 and amendment (a) dated 03 December 2018).

This SAP describes the planned analysis of the safety and tolerability data from this study. A detailed description of the planned TFLs to be presented in the clinical study report (CSR) is provided in the accompanying TFL shell document.

The intent of this document is to provide guidance for the statistical analyses of data. In general, the analyses are based on information from the protocol, unless they have been modified by agreement between Eli Lilly and Company and Covance Early Clinical (EC) Biometrics. A limited amount of information concerning this study (e.g., objectives, study design) is given to help the reader's interpretation. This SAP must be signed off prior to first subject administration for this study. When the SAP and TFL shells are agreed upon and finalized, they will serve as the template for this study's CSR.

This SAP supersedes the statistical considerations identified in the protocol; where considerations are substantially different, they will be so identified. If additional analyses are required to supplement the planned analyses described in this SAP, they may be performed and will be identified in the CSR. Any substantial deviations from this SAP will be agreed upon between Eli Lilly and Company and Covance EC Biometrics and identified in the CSR. Any minor deviations from the TFLs may not be documented in the CSR.

This SAP is written with consideration of the recommendations outlined in the International Conference on Harmonisation (ICH) E9 Guideline entitled Guidance for Industry: Statistical Principles for Clinical Trials and the ICH E3 Guideline entitled Guidance for Industry: Structure and Content of Clinical Study Reports.

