# 12. CHANGES FROM THE PROTOCOL SPECIFIED STATISTICAL ANALYSES

There were no changes from the protocol specified statistical analyses.

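### SAP 9.3.9 omits injection-site bleeding/bruising from the summaries that protocol 10.3.1.2.2 calls for, while SAP 12 declares no change from the protocol

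*SAP*

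**What the plan says.** Protocol 10.3.1.2.2 sets out what is to be done with "injection-site assessments, including pain, induration, swelling, pruritus, bleeding/bruising, and erythema/redness. The parameters will be listed and summarized using standard descriptive statistics". The synopsis says the same. Protocol 9.4.5.2 makes bleeding/bruising an assessment of its own: a blinded assessor observes every injection site at the scheduled times, and "the presence of visible bleeding/bruising will be recorded on the eCRF".

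SAP 9.3.9 reads "Injection sites will be assessed for induration, swelling, pruritus, and erythema/redness", and provides a frequency table by formulation and a listing for those data. SAP 9.3.10 deals with pain. No section of the supplied SAP text refers to bleeding or bruising.

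Three general provisions of the SAP decide what follows from that silence:

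- SAP 9.1: "Summary statistics and statistical analysis will only be presented for data where detailed in this SAP". The same section promises listings of everything in the database.
- SAP 3: "This SAP supersedes the statistical considerations identified in the protocol; where considerations are substantially different, they will be so identified".
- SAP 12: "There were no changes from the protocol specified statistical analyses".

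**The concern.** A programmer working from the SAP would produce a listing of bleeding/bruising and no table. The protocol promised both, and the SAP does not say that one has been dropped.

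What is at stake is modest but not empty. Protocol 5.1 counts bleeding/bruising assessments among the means of monitoring safety and tolerability, and protocol 7.3 requires blinded staff for them. According to protocol 3.1, neither test formulation had previously been given to humans or animals. Without a table, a reader who wants to compare the formulations on this sign must count from the listing. Protocol 10.3 also requires any change of analysis method, with its justification, to be described in the study report. A SAP that declares no change gives the report's authors no prompt to do so.

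**Working it through.** The plan gives no figure to reproduce. The check is a comparison of texts.

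**Step 1. Parameters the protocol says will be summarized, against the SAP.**

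| Parameter in protocol 10.3.1.2.2 | Summary detailed in the SAP |
|---|---|
| Pain | 9.3.10 |
| Induration | 9.3.9 |
| Swelling | 9.3.9 |
| Pruritus | 9.3.9 |
| Erythema/redness | 9.3.9 |
| Bleeding/bruising | none |

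Count: 6 in the protocol; 4 (9.3.9) + 1 (9.3.10) = 5 in the SAP; 6 − 5 = 1 not covered.

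**Step 2. Could the title of SAP 9.3.9 cover it by implication?** Protocol 10.3.1.2.2 does use the term injection-site assessments broadly enough to include bleeding/bruising. SAP 9.3.9, however, fixes its scope by naming signs, and these are exactly the four of protocol 9.4.5.1: "Induration, swelling, pruritus, and erythema/redness associated with study injection sites will be evaluated by the blinded assessor". The protocol keeps bleeding/bruising apart, with its own section (9.4.5.2) and its own row in the Schedule of Activities. The other tests under protocol 9.4.5 each have a counterpart in the SAP:

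- 9.4.5.1 injection-site signs: SAP 9.3.9
- 9.4.5.2 bleeding/bruising: none
- 9.4.5.3 pain: SAP 9.3.10
- 9.4.5.4 C-SSRS: SAP 9.3.7
- 9.4.5.5 HADS: SAP 9.3.8

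Four of five are carried over. The implied reading does not fit this pattern.

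**Step 3. Does the timing of the versions explain it?** The SAP is dated 8 January 2019 and was written against the original protocol and amendment (a). The protocol supplied is amendment (b). The revised sections shown in protocol Appendix 6 include neither 9.4.5.2 nor 10.3.1.2.2, so the requirement appears to have been in place when the SAP was written.

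**Step 4. What the SAP's rules then produce.** Under SAP 9.1 the data are listed because they are in the database, and not summarized because the SAP does not detail a summary. Under SAP 3 the SAP prevails over the protocol's statistical text. Under SAP 12 the difference is not declared.

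**Step 5. Do the adverse-event tables fill the gap?** Only in part. Bleeding or bruising reported as an adverse event would enter the by-formulation tables of SAP 9.3.1. Protocol 9.4.5.1, though, makes an injection-site reaction an adverse event only if it is clinically significant or the subject volunteers it. Routine positive observations at scheduled times need not appear there.

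**The case against.** The strongest reply is that this is a gap in wording and not yet a gap in reporting. SAP 3 places the detailed description of outputs in the TFL shells, which were not supplied and may already hold a bleeding/bruising table. SAP 3 also bases analyses on the protocol in general, and allows supplementary analyses if the study report identifies them. This stands. It is why the conclusion is limited to what the SAP text provides. It does not rescue that text: SAP 9.1 still calls for no such summary, and SAP 12 is still inaccurate.

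It may also be said that bleeding/bruising is only one of many monitored items, and that the SAP gives abnormal laboratory values a listing alone. The laboratory comparison does not help, because protocol 10.3.1.2.2 promises only a listing for laboratory values but both a listing and a summary for bleeding/bruising. The point about importance does stand. Table RHCS.1 gives the exploratory endpoints as TEAEs, SAEs, ISRs and VAS pain scores, and the planned interim review covers AEs, VAS and ISR data. Neither names bleeding/bruising.

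A reader might infer more than the documents support:

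- **That the study report would be silent on how often bleeding/bruising occurred.** It would not. The listing remains, and occurrences can be counted from it; only the tabulation is missing.
- **That the summary was deliberately dropped or concealed.** Nothing shows such a decision. A drafting oversight, with the protocol's summary still intended, fits the texts equally well.
- **That the exploratory comparison of formulations is compromised.** The endpoints named for it are unaffected.

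**Conclusion.** The mismatch holds. The protocol plans a descriptive summary of six injection-site parameters and the SAP details five. Bleeding/bruising is left with a listing, and the SAP 12 statement is wrong to that extent.

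The size is one of six protocol-named parameters and one descriptive tolerability output. The primary VAS analysis is not affected, and no estimate or inference changes. The documents give no event rate for bleeding/bruising, so the number of findings left untabulated cannot be stated. Multiplying scheduled assessments by planned subjects would count observation times and would not measure information lost. Severity is minor.

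The conclusion rests on the SAP text as supplied. If the shells contain the table, the practical loss disappears and what remains is a correction to SAP 9.3.9.

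**What to change.** Add bleeding/bruising to the signs named in SAP 9.3.9, so that it enters the same frequency table by formulation and the same listing. The data are already recorded on the eCRF. The protocol asks only for standard descriptive statistics, so the layout used for the other four signs is enough.

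If a listing alone is intended, say so in SAP 12 and give the reason. If the SAP is not to be reissued, SAP 3 allows the table to be produced as a supplementary analysis, identified as such in the study report. If the shells already contain it, bring the SAP text into line with them.

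Counts at each time point, attribution of Day 21 and Day 43 findings to a formulation through the documented sites, and explicit counting rules for the other signs are optional refinements that this point does not require.

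The cost is a few words in the SAP and one more item in a descriptive table. No new data are needed and the primary analysis is untouched.

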#### 9.3.10 Injection Site Pain Assessment

Pain measurements will be quantified using the 100-mm VAS pain score (100-mm line anchored by verbal descriptors, usually "no pain" and "worst imaginable pain) for all subjects, whether or not they report injection pain.

Final, 8 January 2019 Page 8 of 10

VAS pain score will be summarized using standard descriptive statistics. In addition, the severity of pain will be categorized by VAS pain score as: mild pain ( $\leq$ 30), moderate pain ( $\geq$ 30 and  $\leq$ 70), and severe pain ( $\geq$ 70). The number and percentage of the subjects in each pain severity category will be summarized by formulation and time point. Figures of the continuous injection-site pain VAS score will also be presented, by formulation and measuring time point.

A mixed-effects repeated measures analysis model will be used to analyze the continuous injection-site pain VAS score by each time post-injection (0, 10, 20, 30, and 60 minutes). For measures at each time post-injection, the model will include formulation, period (Day 1, Day 8, or Day 15), formulation sequence, and formulation by formulation sequence as fixed effects. The covariance structure of the model will be unstructured. The Kenward-Roger method will be used to estimate the denominator degrees of freedom. Type III sums of squares for the least squares means will be used for the statistical comparison; formulation differences on every time point will be reported, along with the corresponding 95% confidence intervals for the differences. All pair-wise formulation comparisons by measuring time point will be evaluated and presented.

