Abnormal lab values will be listed. Other safety parameters that will be assessed include injection-site assessments, including pain, induration, swelling, pruritus, bleeding/bruising, and erythema/redness. The parameters will be listed, and summarized using standard descriptive statistics. Suicidal ideation and/or behavior and self-injurious behavior with no suicidal intent, based on the C-SSRS, will be listed by subject. HADS item scores will be listed for subjects with HADS depression subscale ≥ 11 at any time. Additional analyses may be performed if warranted upon review of the data.

VAS pain score will be summarized using standard descriptive statistics. In addition, the severity of pain will be categorized by VAS pain score as: mild pain (\leq 30), moderate pain (>30 and \leq 70), and severe pain (>70). The number and percentage of the subjects in each pain severity category will be summarized by treatment and time point.

2. Schedule of Activities

Study Schedule Protocol I1F-MC-RHCS

Study Schedu	Screening	-	Study Day											Comments
Procedure	-28 to -2 days prior to Day 1	Day -1	Day 1	Day 7	Day 8	Day 14	Day 15	Day 21 (± 1 day)	Days 28 & 35 (± 3 days)	Day 43 (± 3 days)	Days 50, 57, & 64 (± 3 days)	Day 71 (± 3 days)		
Informed Consent	X													
Subject Admission to CRU		X		X		X								
Subject Discharge from CRU			X		X		X							
Safety Assessment (Telephone Call)									X		X	X		Every effort will be made to contact subjects as near to this time as possible but missed calls will not be recorded as protocol deviations.
Medical History and Demographics	X													
Height	X													
Weight	X	X											X	
Serology	X													
QuantiFERON® -TB Gold or TST	X													
Randomization			X											

	Screening						Study Da	ay					FU/ ED ^a	Comments
Procedure	-28 to -2 days prior to Day 1	Day -1	Day 1	Day 7	Day 8	Day 14	Day 15	Day 21 (± 1 day)	Days 28 & 35 (± 3 days)	Day 43 (± 3 days)	Days 50, 57, & 64 (± 3 days)	Day 71 (± 3 days)		
Investigational Product Administration			X		X		X							
Ethanol Testing and Urine Drug Screen	X	X		X		X								May be repeated at the discretion of the investigator.
Pregnancy Test (Females Only; as applicable)	X	X		X		X							X	Serum pregnancy test will be performed at screening. Urine pregnancy test will be performed at all subsequent time points.
FSH Test	X													Females only, if applicable.

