3.3. Benefit/Risk Assessment

As this study will enroll healthy subjects, there is no anticipated therapeutic benefit for the subjects.

As of the cut-off date for the current Investigator's Brochure (IB; 22 March 2018), more than 8755 clinical trial subjects have received at least 1 dose of ixekizumab (5934 patients with Ps,

532 patients with rheumatoid arthritis, 1301 patients with psoriatic arthritis, 119 healthy subjects, and an estimated 869 patients with axial spondyloarthritis).

Forty-one healthy subjects were administered ixekizumab by PFS (160 mg [2 × 80 mg] followed by 80 mg 2 weeks later) in Study I1F-MC-RHCA (Study RHCA). All adverse events (AEs) in Study RHCA were mild in severity. The most commonly reported AEs were headache, injection-site erythema, and fatigue. With the exception of fatigue, this is consistent with commonly reported AEs reported in Phase 3 trials. An additional 78 healthy subjects were administered ixekizumab by PFS, marketed AI, and modified AI (3 single 80 mg doses) in Study I1F-MC-RHCK. All treatment-emergent AEs (TEAEs) were mild in severity and the most commonly reported TEAEs were ISRs, injection site pruritus, nausea, diarrhea, upper respiratory tract infection, and injection-site erythema. Pharmacokinetic simulations (described further in Section 5.5) show that the 80 mg dose given every week for a total of 3 injections proposed for this study is projected to give exposures that are within the range of exposure to ixekizumab reported in previous studies, thus a similar TEAE profile is expected. The excipients are expected to be safe and well tolerated.

More information about the known and expected benefits, risks, serious AEs (SAEs) and reasonably anticipated AEs of ixekizumab are to be found in the IB.

4. Objectives and Endpoints

Table RHCS.1 shows the objectives and endpoints of the study.

Table RHCS.1. Objectives and Endpoints

Objectives	Endpoints
Primary	
Evaluate pain intensity on injection of ixekizumab with	Visual analog scale (VAS) pain score immediately
different formulations.	(within 1 minute) after injection
Exploratory	
To evaluate the safety and tolerability of a single 80 mg	TEAEs, SAEs, ISRs, and VAS pain scores
SC dose of ixekizumab Test Formulation 1 and Test	
Formulation 2 formulations compared to the commercial	
formulation (Reference)	

5. Study Design

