9.4.5.3. Injection-Site Pain

Pain measurements will be quantified using the 100-mm VAS pain score for all subjects. The VAS is a well-validated tool (Williamson and Hoggart 2005) to assess injection-site pain; it is presented as a 100-mm line anchored by verbal descriptors, usually "no pain" and "worst imaginable pain." The subject will be asked to relate any pain at the injection site on a scale of 1 to 100 mm on the line immediately (within 1 minute) following injection and at the time points listed in the Schedule of Activities (Section 2).

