10.3.1.2. Statistical Evaluation of Safety

10.3.1.2.1. Injection-Site Pain

VAS pain score will be summarized using standard descriptive statistics. In addition, the severity of pain will be categorized by VAS pain score as: mild pain (\leq 30), moderate pain (\geq 30 and \leq 70), and severe pain (\geq 70). The number and percentage of the subjects in each pain severity category will be summarized by treatment and time point.

A mixed-effects repeated measures analysis model will be used to analyze the continuous injection-site pain VAS score by each time post-injection (0, 10, 20, 30, and 60 minutes). For measures at each time post-injection, the model will include treatment, period (Day 1, Day 8, or Day 15), treatment sequence, and treatment by treatment sequence as fixed effects. The covariance structure of the model will be unstructured. The Kenward-Roger method will be used to estimate the denominator degrees of freedom. Type III sums of squares for the least squares means will be used for the statistical comparison; treatment differences on every time point will be reported, along with the corresponding 95% confidence intervals for the differences. All pair-wise treatment comparisons by measuring time point will be evaluated and presented.

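### The VAS severity table has no row for no pain, so pain-free subjects are counted as having mild pain and the pain-free share by formulation is not shown

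*SAP*

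**What the plan says.** SAP 9.3.10 obtains a VAS score "for all subjects, whether or not they report injection pain". The instrument is a "100-mm line anchored by verbal descriptors, usually 'no pain' and 'worst imaginable pain". In the same section "the severity of pain will be categorized by VAS pain score as: mild pain" for scores up to 30, followed by a moderate band up to 70 and a severe band above that. Mild has no lower limit. Protocol 10.3.1.2.1 and the Statistical Analysis part of the synopsis use the same three bands, and none of these places has a band for no pain.

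The planned output in the SAP is: "The number and percentage of the subjects in each pain severity category will be summarized by formulation and time point". Protocol 10.3.1.2.1 has the matching sentence: "The number and percentage of the subjects in each pain severity category will be summarized by treatment and time point". The time points are 0, 10, 20, 30 and 60 minutes after injection.

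Two other statements bear on the point. Protocol 9.4.5.3 asks the subject to "relate any pain at the injection site on a scale of 1 to 100 mm on the line", so the stated range starts at 1 although the lower anchor is the absence of pain. Protocol Section 4 (Table RHCS.1) makes the primary endpoint the "Visual analog scale (VAS) pain score immediately" after injection, that is, the score itself and not a severity band.

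**The concern.** Everyone is scored, including subjects who feel nothing, and every band is named as a degree of pain. The three rows of the table therefore account for 100% of assessed subjects as having some pain, at every time point and for every formulation, whatever the data are.

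The study was set up because a change of buffer might address reported injection-site pain. A move from slight pain to none would be a direct sign of that, and it happens entirely inside the mild row. If many later scores lie near the lower end, which is plausible but not stated in the documents, all three formulations could read close to 100% mild.

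**Working it through.** The documents state no pain-free rate and no VAS distribution, so there is no figure of the plan's to reproduce. The check is of the classification rule, followed by an illustration.

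**Step 1: apply the rule.** Mild means VAS ≤ 30.

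| VAS | Band |
|---|---|
| 0 | mild |
| 1 | mild |
| 5 | mild |
| 31 | moderate |
| 71 | severe |
| 100 | severe |

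The result is the same with the synopsis cut-offs and with those in SAP 9.3.10. The two texts as supplied differ only at scores of exactly 30 and 70. That may come from the text extraction, and this point does not depend on it.

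**Step 2: what the mild row contains.** Reported mild = pain-free + truly mild. Only the sum is printed, so any split between the two gives the same table.

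**Step 3: illustration.** Take n = 78 per formulation, the planned number of completers in SAP Section 7 (3 × 26). The pain-free shares are assumptions, and all scores are taken as 30 or less.

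| Assumed pain-free shares | Planned table, mild | Split table, no pain | Split table, mild |
|---|---|---|---|
| 20% vs 50% | 78/78 vs 78/78 | 0.20 × 78 ≈ 16 vs 0.50 × 78 = 39 | 78 − 16 = 62 vs 78 − 39 = 39 |
| 10% vs 30% | 78/78 vs 78/78 | 0.10 × 78 ≈ 8 vs 0.30 × 78 ≈ 23 | 78 − 8 = 70 vs 78 − 23 = 55 |

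If instead 60% of subjects score 30 or less (0.60 × 78 ≈ 47), and the pain-free are anywhere from 0% to 50% of all subjects (0 to 39), truly mild pain runs from 47 down to 47 − 39 = 8. The planned table prints 47 throughout. The moderate and severe counts do not move.

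**Step 4: look for the pain-free share elsewhere.** SAP 9.1 lists mean, SD, median, minimum, maximum and N for continuous data. SAP 9.3.9 tabulates induration, swelling, pruritus and erythema, but not pain. Protocol 10.3.1.2.2 names pain among the injection-site assessments but defines no count of present against absent. Individual scores will be listed, so the share could be worked out later, but it is not a planned result.

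**Step 5: which score means no pain.** If the recorded range starts at 1, as Protocol 9.4.5.3 reads, a row defined as 0 mm would be empty and the pain-free subjects would stay in the mild row. If 0 can be recorded, the row works at 0. The documents do not settle this.

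**The case against.** The strongest reply is that the signal is largely visible elsewhere. The severity table supplements the continuous score. SAP 9.3.10 also plans descriptive statistics, figures by formulation and time point, and mixed-model differences with 95% confidence intervals for every pair at all five times, and a shift from slight pain to none lowers those statistics. In the 20% against 50% illustration, taking no pain as 0 and n = 78, the median is the average of the 39th and 40th ordered scores. With 39 zeros it is half the smallest positive score. With 16 zeros it averages the 23rd and 24th of the 62 positive scores, well inside the positive range. That contrast would usually show.

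This largely stands, and it limits the point to one table. What it does not supply is the pain-free percentage, which no planned summary gives, nor does it correct the label.

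Two further replies have some weight. The number of bands in a descriptive table is partly a presentation choice, and the detailed layouts are in a TFL shell document that is not available here. However, the SAP text itself defines the bands, and under it a pain-free subject is labelled as having mild pain. The other reply is timing: the SAP is final (8 January 2019), and Protocol Appendix 6 reports about 80% of the VAS data collected when enrolment was paused. A change of bands now has to be declared, which shapes the fix below.

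A reader might infer that the plan overstates pain in general, or tilts the comparison of formulations. The documents do not support either reading. The primary endpoint and the model use the score itself, and the same banding applies to all three formulations.

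**Conclusion.** The point holds as a labelling and reporting gap in a supplementary table. By the stated rule, pain-free subjects are counted as having mild pain, so the count with mild (any) pain is overstated by exactly the number who are pain-free, and a difference in the pain-free share cannot be seen there, however large. Means, medians, figures, model-based differences and the moderate and severe counts are unaffected.

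The classification result needs no assumption about the data. The size in practice cannot be derived: the pain-free shares used above are assumed, and 78 is the planned number of completers, which may not be reached because Protocol Appendix 6 says that enrolment of new subjects was stopped. This is a minor improvement and does not threaten the study's main conclusion.

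**What to change.** 1. Reconcile the 1-to-100 range in Protocol 9.4.5.3 with the lower anchor of the line. State whether 0 can be recorded and which recorded score means no pain, judged from how the scale was administered and recorded and not from results by formulation.
2. In SAP 9.3.10 and Protocol 10.3.1.2.1, and in the synopsis to match, add a no-pain row at that score and define mild as above it and up to 30.
3. Keep a combined row for all scores up to 30, so that the planned table can still be read.
4. Settle the cut-offs at 30 and 70 in the same edit, so that the synopsis, Protocol 10.3.1.2.1 and SAP 9.3.10 agree.
5. Because about 80% of the VAS data had been collected by amendment (b), identify the row in the clinical study report as an added summary. SAP Section 3 and Protocol 10.3 both allow for additional analyses.

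The cost is one extra row per formulation and time point from data already collected, a clarification of the scale, and a note in the report. No new assessment and no change to the model are needed.
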